6.1.2 SCREENING

Assessment of suicide risk (SR) and other safety issues are addressed by the intake counselor during the intake session across all participating sites. When the student meets for the intake session, as part of routine intake procedures, they will complete the Counseling Center Assessment of Psychological Symptoms (CCAPS-62). If the student selects a 2 or above on the question, “I have thoughts of ending my life,” (range is 0 “not at all like me” to 4 “extremely like me”) or endorses suicidality on other intake questionnaires or via self-report to the counselor the intake counselor will give the student a brief explanation of the study. Intake counselors will complete the Screening Data Form to assess basic inclusion and exclusion criteria. If a student meets all inclusion and no exclusion criteria and is interested in participating in the study, the PC will be notified, and an appointment will be scheduled with the research team for consenting (an e-consent process will be used) and a baseline assessment, which may be remote or in-person. If conducted remotely, the IE will reach out to the student ahead of the appointment with a link to a secure telehealth videoconferencing meeting. For students who decline to participate, the intake counselor will document reasons for declining participation.

6.1.3 BASELINE

The baseline assessment is conducted by the IE, either online or in person. The IE will first review the e-consent in detail with the student and answer any questions. The IE will confirm that the student agrees with: (1) being randomized to one of two treatments; (2) the possibility of proceeding in an “adaptive” manner—ending treatment/going into maintenance or being randomized to one of two treatments for up to 8 additional weeks; (3) possibly participating in a group (if assigned to DBT); (4) completing assessments even if no longer in treatment; (5) providing information to create a unique identifier; and (6) having their therapy sessions video-recorded. After consent is obtained, questionnaire/interview baseline assessments will be conducted by the IE (see Table 1). At the end of this assessment or within 1 business day, student participants will receive confirmation of who their counselor will be and the date of their first teletherapy/in-person appointment (typically within 7 days after the baseline visit, but clinical concerns will take precedence). Students who decline participation prior to giving consent, or who enroll but later choose to withdraw from the study, will have access to the usual care at the CCC (Note: all randomized student participants will be included in the ITT analyses).

6.1.4 RANDOMIZATION

Following the completion of the baseline assessment, the site PC will review the consent, document the randomization block variables (gender, medication, past suicide attempt), obtain randomization assignment from the Data Center at Duke University, and reveal randomization results to an already assigned counselor. Note that student participants will learn of their treatment assignment by the counselor at their first treatment visit (this procedure was used in the pilot project and received very favorably by students and counselors).

6.1.5 STUDY INTERVENTION DESCRIPTION

Study interventions include Treatment as Usual (TAU), the Collaborative Assessment and Management of Suicidality (CAMS), or CC-DBT.

TAU: Treatment as Usual consists of normal College Counseling Center (CCC) therapeutic procedures. TAU will allow counselors to determine level of care and therapeutic modality depending on the needs of the participant.

CAMS: CAMS is an evidence-based, suicide focused approach⁶¹ that was first developed and studied in a CCC specifically for college students.⁶² CAMS is a problem-focused treatment that targets client-defined suicidal “drivers” or issues that lead to SI.⁷ Central to CAMS is the use of the Suicide Status Form (SSF), a multipurpose clinical assessment, treatment planning, tracking, and outcome tool.⁷ The SSF serves as a clinical roadmap to guide collaboration as counselor and client sit next to each other exploring SR through quantitative/qualitative assessments and suicide-specific treatment planning. All CAMS sessions begin with a consideration of the “SSF Core Assessment.” Sessions then focus on the CAMS Stabilization Plan (CSP) and the client’s suicidal drivers. All sessions end by updating the CSP and problem-focused care targeting suicidal drivers. CAMS is theoretically agnostic; counselors use their own approach to treating client-identified suicidal drivers.

CC-DBT: DBT^{8,29} is an empirically validated treatment for complex clinical presentations, including BPD, SI, and NSSI. DBT (which includes individual therapy, skills group, and peer consultation for counselors) produces gains for suicidal BPD clients across a variety of domains, including SI, BPD, SAs, NSSI, hospitalizations, and social functioning.^{15,72} DBT is based on a skills deficit model that suggests that BPD is a disorder of emotion dysregulation stemming from important deficits in interpersonal, emotion regulation, and distress tolerance skills. Suicidal behavior is viewed as maladaptive problem-solving behavior reinforced by either an immediate reduction in emotional arousal and/or by the environment’s response.²⁹ Thus, DBT focuses on teaching skills, particularly emotion regulation, and facilitating the replacement of maladaptive behaviors with skillful behavior. We will use an adaptation of DBT, CC-DBT, that is designed to disseminate within CCCs. Participants will receive up to 8 weeks of individual CC-DBT sessions as well as 6 weeks of DBT skills training. Counselor participants will attend weekly consultation team meetings. CC-DBT includes key DBT elements such as orienting clients to the treatment model, using a diary card to monitor problematic behaviors, relying on a hierarchy of targets to guide treatment at each session, and conducting chain and solution analyses to determine and address controlling variables of problematic behavior will be followed.¹⁴⁵

Stage 1: Student participants will initially be randomized to TAU or CAMS. The duration of Stage 1 treatment will range from 4-6 weeks.

Stage 2: Non-responders to Stage 1 Treatments will be randomized into either CAMS or CC-DBT. The duration of Stage 2 treatment will range from 1-8 weeks.

6.1.6 ADMINISTRATION AND/OR DOSING

Treatment dosage for Stage 1 will consist of prescribed weekly sessions for up to 6 weeks for TAU or CAMS, followed by up to 8 weeks of CAMS or CC-DBT. It is assumed that weekly sessions align with typical CCCs. The counselor (interventionist) will be trained on CAMS and CC-DBT and will be evaluated for fidelity of implementation throughout the study. Length of time (e.g., student participant weeks in treatment) will be determined based on student participant responsiveness to their assigned treatment condition.

Except for the CC-DBT skills group and possibly other CCC therapy groups in the TAU condition, student participants will have no contact with other student participants, as this is an individualized treatment per each student participant.

Management of Student Participants in the Maintenance Phase. Student participants who are classified as responders during either stage 1 or stage 2 will end active study treatment and enter maintenance. Students may continue to receive CCC services during study maintenance. Students will continue to complete regularly scheduled IE assessments and remain in maintenance until the end of their study participation at 26 weeks. During the maintenance phase, the study team will contact students every four weeks. The four-week contact schedule will continue until their final assessment point. It is possible that students may experience a relapse in suicidality during the maintenance phase, which may be reported during the scheduled IE assessments, in response to a 4-week contact, or by the student spontaneously contacting a member of the CAMPUS trial clinical or research team. In these instances, students will be referred to their CCC for standard care. As noted elsewhere in this protocol (see section 6.5), treatments received outside of the study will be documented via the treatment history interview (THI).

Management of College Session Breaks. CAMS and CC-DBT individual sessions will be conducted either in-person or remotely via a HIPAA-compliant telehealth platform. Thus, management of treatment during short breaks will not be difficult. The end of an academic term often serves as a natural and longer-term break in treatment in CCCs. Given the nature of the academic calendar, participants may take a “break” from the study treatment while they are on academic breaks if they are unable or ineligible to receive CCC services (e.g., residing out of state for the summer), and then continue where they left off upon return. This is an essential adaptation to the setting, and it has been considered in terms of recruitment rates and will also

be considered in the analyses (e.g., dosage defined as number of sessions and not time since randomization per stage; number of additional treatment sessions received).

6.2 FIDELITY

6.2.1 INTERVENTIONIST TRAINING AND TRACKING

Initial Suicide-Focused Treatments Training. During the training phase, the counselor participants will be asked to read manuals for CAMS⁷ and DBT,^{8,29} participate in a 3-hour online orientation to the study, and then 12-hours of CAMS remote training and 25-30-hours of DBT remote or in-person training, spread over multiple days. Each site will also have weekly DBT peer consultation team meetings. Remote consultation from DBT and CAMS experts will occur more frequently (e.g., weekly) when the trial begins and will occur less frequently as consultation teams grow in skill.

Counselor participants joining the study after the first study year will receive the same type and intensity of training (3-hour orientation to the study, 12-hours of remote CAMS training, and 25-30 hours of DBT training) as other counselor participants but the timing and delivery of the trainings will be dictated each year, based on the number of new counselor participants and their availability.

Certification Requirements. Participant counselors' first randomized case will be supervised more closely as a certification case. If a counselor does not receive satisfactory ratings on their certification case, an individualized adherence plan will be created with the therapist and DBT/CAMS experts. Any concerns about ongoing problems with counselors meeting adherence standards will be discussed with the QA committee. Under rare circumstances, counselors who consistently do not meet adherence standards may be asked to not provide a specific treatment or to leave the study.

Treatment Adherence to CAMS and DBT. All treatment sessions will be digitally recorded. During the counselor training phase, counselors will participate in weekly remote group consultation/supervision (CAMS or DBT), which will be supplemented with individual site-level remote supervision as needed. A Standardized Operating Procedure (SOP) will be developed for certifying that counselors are adherent to CAMS and DBT treatment protocols. Following the training phase, two sessions will be randomly selected to be rated for adherence per DBT student, one from the first two sessions and one from the remaining sessions. A random sample of 10% of DBT skills group sessions will be selected for rating. For CAMS sessions in Stage 1, the first session will be rated for adherence and one other session will be randomly selected from the other sessions for adherence rating. For CAMS sessions in Stage 2, the first session after re-randomization into CAMS will be selected for rating and then one other session will be randomly selected. Feedback will be provided to counselor participants (but not in real time) and tallied in terms of percent of time counselor participants met minimal (DBT) or satisfactory (CAMS) adherence.

6.3 MEASURES TO MINIMIZE BIAS: RANDOMIZATION AND BLINDING

Randomization

We will rely on an adaptive-biased coin design¹⁰⁹ to attempt to balance conditions at each stage based on gender, previous suicide attempt(s), and current psychotropic medications. At Stage 2, the PC will obtain information on the blocking variables, along with the tailoring variable, from counselors and the electronic medical record (EMR; Titanium for all sites) prior to randomization. The PC at each site will randomize subjects via the centralized database using a customized system tailored for the SMART design housed at the Duke Data Center.

All assessments of the main endpoints will be performed by the independent evaluators (IEs), who will remain blind to treatment status. It is always possible that student participants could tell the IE during their assessments about the type of therapy they have been receiving. To mitigate this risk, all student participants will be reminded about the importance of not telling the IEs which treatment they received. It is also possible that counselor participants could tell the IE which treatment condition a particular student participant is in; counselor participants will be frequently reminded not to do so. To evaluate how well blinding was maintained, the IEs will be asked to indicate what treatment group(s) they thought the student participant belonged to at the end of stage 1 and, if applicable, at the end of stage 2.

6.4 STUDY INTERVENTION/EXPERIMENTAL MANIPULATION ADHERENCE

Student participant adherence will be tracked through EMR systems at each site including weekly therapeutic sessions.

6.5 CONCOMITANT THERAPY

If it is discovered during or after the study that a participant received a “crossover-treatment” on his/her own or received any other form of therapy, we will document these treatments in the clinical record and on the treatment history form that is completed by the student participant and the IE and develop procedures to minimize this threat as much as possible for use in the large-scale trial.

While clinical and research staff are expected to strongly discourage treatment outside the study, these student participants will continue to be treated within their assigned treatment arm. Stated differently, student participants receiving non-protocol treatments on their own accord are not automatically considered premature terminators. On the other hand, student participant-initiated crossover treatments should prompt consideration of a review of the student participant’s clinical status. An example of this would be the case of a student participant-initiated psychiatric hospitalization for worsening depression, which would automatically lead to premature termination.

Handling of Medications. Student participants will neither be asked to discontinue medications or to start medications as part of the study. Following regular CCC practice, student participants may be referred for a psychiatric consultation if needed. We will stratify on current use of psychotropic medication at both randomization points to equate medication use across

conditions. We will also assess for any mid-treatment use of medications via data collected on the treatment history interview. Approximately a quarter of students presenting to a CCC are already on a psychiatric medication.⁴² This approach to medication reaches a good balance of allowing for medications while not including an active protocol on psychotropic management and it seems appropriate, given the limited evidence of pharmacotherapy-only treatment for SR.¹⁴⁸

7 STUDY INTERVENTION/EXPERIMENTAL MANIPULATION DISCONTINUATION AND PARTICIPANT DISCONTINUATION/WITHDRAWAL

7.1 DISCONTINUATION OF STUDY INTERVENTION/EXPERIMENTAL MANIPULATION

Involvement in this study will be completely voluntary, and participants may withdraw from the study at any time. Withdrawal from the study will not prohibit student participants from continuing to receive counseling services from their college counseling center or counselor participants from continuing with their normal job duties at the CCC. If the potential student participant shows a lack of interest during intake and consent procedures, the intake counselor will drop the subject. Consent is an ongoing process, so as the study progresses, counselors will be instructed to contact the PC or the PI if the student participant expresses any concerns about continued participation and the PC or PI will be available to meet with the student participant and/or his/her counselor to discuss any concerns regarding continued student participation throughout the study.

Missing four consecutive “scheduled” treatment sessions without any contact with the research team or study counselor will constitute treatment dropout. (Note: attempts will be made to continue collecting outcome data on all student participants who are considered treatment dropouts.) Student participants who are contacted and inform the study team that they no longer wish to provide assessment data will be considered to have withdrawn consent and therefore meet the definition of a study dropout. For more detailed operational definitions, see section 7.2 below.

7.2 PARTICIPANT DISCONTINUATION/WITHDRAWAL FROM THE STUDY

Participants are free to withdraw from the study at any time upon request. An investigator may discontinue or withdraw a participant from the study for the following reasons:

- Death of participant.
- Participant withdraws from the school.
- Acute, chronic, or long-term physical or psychiatric illness in the participant leading to inpatient hospitalization during the study.
- Any clinical AE, onset of new medical condition or other situation that occurs such that continued participation in the study would not be in the best interest of the participant.

As with many other long-term studies, we will experience multiple scenarios of participant attrition. To develop procedures to appropriately manage these scenarios consistently across the sites, the various types of attrition have been defined below.

- A. **Study Dropout** (aka Withdrawal of Consent). Study dropout refers to a student participant who withdraws from the assessment portion of the study. A student participant who drops out of the assessment component is not eligible to receive study treatment.
- B. **Treatment Non-Compliance**. Treatment non-compliance pertains to a student participant who continues to participate in the treatment and assessment components of the study, but often fails to follow the study treatment procedures (e.g., refuses to appropriately engage in therapy or tends to miss treatment sessions, etc.). Such student participants have not withdrawn consent (those that do withdraw consent are classified as Study Dropouts) for either the treatment or assessment components, but simply have failed to fully participate in the assigned treatment arm.
- C. **Treatment Dropout**. Treatment dropout pertains to a student participant who has withdrawn consent for the treatment component only. By definition, a treatment dropout is a student participant who is no longer willing to participate at all in his/her assigned treatment but is willing to participate in the assessment component.
- D. **Premature Termination**. Premature termination refers to a student participant for whom the clinical team recommends additional treatment above what can be provided in the assigned treatment arm as randomized. The student participant, however, continues to participate in the assessment component and, insofar as possible, in the treatment component of the study.

Premature termination occurs when the student participant deteriorates or develops an urgent clinical crisis that leads the clinical team to recommend the termination from the assigned study treatment as randomized. Such cases are equivalent to “investigator-initiated protocol violators.” Premature termination from the assigned treatment arm simply means that the assigned treatment is no longer adequate to meet the clinical needs of the student participant. It does not necessarily mean that the intervention within the assigned treatment has been discontinued.

The reason for student participant study dropout, treatment dropout, and premature termination will be recorded. Consistent with intention-to-treat principles, student participants who sign informed consent and to whom randomization is revealed but do not receive the study intervention (e.g., choose to study drop before starting treatment) will not be replaced. Likewise, student participants who sign informed consent and are randomized and receive the study intervention but subsequently drop out of the study, or are prematurely terminated from the study, will not be replaced.

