CCCs are the front line for mental health services for growing numbers of suicidal students.^{22,41} Yet CCCs face limited resources⁴² and higher demand for services with increasingly complex cases,^{21,43} with more than half reporting that waitlists develop within a few weeks and last throughout the term.²⁵ Despite aspiring to provide only brief therapy,²² data show that in practice CCCs are providing 20 sessions or more to a segment of their student population,⁴⁴ 20% of students have been shown to use 50% of counseling resources,⁴⁵ and highly distressed students appear to need a higher number of sessions.⁴⁶ Suicidal risk (SR) is likely a key culprit of this crisis: one third of treatment seeking students report SI—20% of those at clinical levels in the last year,²¹ SI has become a primary presentation at CCCs,⁴³ CCC resources devoted to “rapid access” services have increased by 28%,²¹ and threat-to-life students use 20-30% more services than other students.²¹ Chronically suicidal students greatly strain CCC resources.^{21,47} The stakes are also high when suicide occurs on a campus.²⁶ CCCs are commonly held directly accountable in malpractice litigation and administrators are realizing that untreated suicidality puts the entire institution at risk. Many severely suicidal students remain in school,²¹ which, in fact, has suicide-protective benefits at a population level.^{48,4} Having a validated, cost-effective, evidence-based approach to treating suicidal students would be very helpful to CCCs.²⁶ Importantly, suicidal college students are not a homogeneous group. They vary in risk and response to treatment and thus a “one size fits all” approach to treatment is not effective for this heterogeneous population.⁵⁰ While many students experience an isolated suicidal episode, 40-50% of severely suicidal students report multiple episodes of SI.⁵¹ In a sample of CCC treatment-seeking suicidal students, 52% quickly resolved suicidality in 6-7 sessions, while others remained suicidal (17%), dropped out of care (22%), or were hospitalized (7%).²⁷ Thus, some suicidal students require more intensive forms of treatment while most respond to briefer forms of care.⁴⁶ It has become imperative to identify an appropriate sequence of evidence-based interventions to address SR in CCCs, matched to different levels of severity and/or responses to treatment, to optimize clinical care and resource efficiency.

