9.3 CAMPUS TRIAL STATISTICAL ANALYSES

9.3.1 GENERAL APPROACH

Overview and Intent-to-Treat. The proposed trial design of adaptive treatment strategies (ATSSs) is like a factorial design;^{156,157,158,159} different analytic subgroups (see Table 8) are combined to answer different questions. Aim 1 is the trial's primary aim; Aims 2-5 are secondary aims and Aim 6 as an implementation aim. All student participants, once randomized, will be included in the intent-to-treat sample, and every effort will be made to collect all primary and secondary outcomes even if a student participant does not engage in randomly assigned treatments. The primary outcome of interest is suicidal risk, which includes suicidal ideation as well as suicide-related behaviors, such as non-suicidal self-injury (NSSI) and suicide attempts (SAs); however suicidal ideation is the primary DV due to relatively low rates of suicidal behaviors post-baseline with college students. Suicides will be tallied as well. All analyses allow for the inclusion of covariates listed as demographics and covariates in Section 8.1. Covariates will enter the model based in clinical importance (gender, age, current alcohol use, current substance use, etc.) and retained on a case-by-case basis based on statistical significance.

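### Section 7.2 lets an investigator withdraw a hospitalised student from the whole study, while other text keeps such students in assessments; where the option is used, outcome-related data may be lost

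*Combined protocol and SAP*

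**What the plan says.** **Text that allows withdrawal from the study.** Section 7.2 of the combined protocol and SAP opens its list with "An investigator may discontinue or withdraw a participant from the study for the following reasons". One listed reason is illness, "physical or psychiatric illness in the participant leading to inpatient hospitalization during the study". Others are leaving school, and a clinical adverse event, new condition or other situation, but only where continuing would not serve the participant's best interest. Section 2.3.3 (Minimizing Risk 1) likewise allows removal from the study of students who worsen significantly, where that is in their clinical interest.

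**Text that keeps such students in assessments.** Section 6.5 gives as an example a "student participant-initiated psychiatric hospitalization for worsening depression, which would automatically lead to premature termination". Section 7.2 D states the consequence: "The student participant, however, continues to participate in the assessment component". Section 7.2 then gives the category a wide scope: "Premature termination occurs when the student participant deteriorates or develops an urgent clinical crisis".

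**Commitments on outcome collection.**
- Section 4.5 promises students who terminate early the same end-of-study assessment as completers.
- Section 6.1.3 has the evaluator confirm at consent that the student agrees to be assessed after treatment has ended.
- Section 9.3.1 puts every randomised student in the intent-to-treat sample and says that "every effort will be made to collect all primary and secondary outcomes", including for students who do not engage with their assigned treatment.

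**The concern.** The same event, a psychiatric admission during the trial, can be handled in two ways, each with support in section 7.2. On one, the student leaves the study. On the other, the student leaves the assigned treatment as randomised but is still assessed. Two sites could act in opposite ways and both be following the protocol, although the attrition definitions are there to make handling consistent across sites.

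The primary outcome is suicidal risk, chiefly the SSI. An admission in this population is likely to be related to it. If assessments stop at that point, whether later scores are missing may depend on what they would have been. The mixed models in section 9.3.2 (Aim 2) and section 9.3.7 (Aim 8) are stated to be unbiased when unobserved values are missing at random. The primary Aim 1 comparison weights by known randomisation probabilities and describes no handling of missing outcomes. Section 9 describes no sensitivity analysis for withdrawal related to outcome.

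**Working it through.** **1. The two paths side by side**

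| Point | Withdrawal list (7.2; also 2.3.3) | Premature termination (6.5, 7.2 D) |
|---|---|---|
| Trigger | Inpatient admission for illness; significant worsening | Student-initiated psychiatric admission for worsening depression; deterioration or urgent crisis |
| What ends | The study | The assigned treatment as randomised |
| Assessments | Not stated | Continue |
| Discretion | Investigator may act | Automatic in the 6.5 example |

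The triggers overlap. Attrition types A to D contain no class for withdrawal by an investigator; only type A, the student's own withdrawal of consent, is defined as leaving assessments. Section 7.2 also speaks of students prematurely terminated from the study, although it defines premature termination as leaving the assigned treatment arm.

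**2. Can earlier scores explain the missingness?** The SSI covers the past two weeks (section 8.1). Evaluator visits are at weeks 0, 3, 6, 10, 14 and 26 (section 4.2), so the gaps are 3, 3, 4, 4 and 12 weeks. A crisis that leads to withdrawal between visits may never enter the SSI record. If the worsening was measured first, the data can still be missing at random.

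**3. Power.** Inputs from section 9.2: 240 per arm, d = 0.30, two-sided 2.5%.

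- Noncentrality: 0.30 × √(240/2) = 3.286; critical value 2.241. Power = Φ(3.286 − 2.241) = 85.2%. The stated 85% reproduces.
- Section 2.1.1 cites 7% hospitalised in an earlier counselling-centre sample. This is a background figure, not a planning rate. 0.07 × 480 = 33.6, about 34 students, leaving 223 per arm. If all were lost, power would be 82.3%.
- Over an assumed 2% to 10% lost, power runs from 84.4% to 81.0%.

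**4. Bias.** Let p be the share of an arm that is withdrawn and D the excess SSI of those students over the rest. If they are dropped altogether, the arm's mean is understated by p × D, so the arm difference shifts by (p₁ − p₂) × D. The target is 0.30 × 7 = 2.1 SSI points (SD 7, section 9.2). All arm rates and values of D below are assumptions.

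| Withdrawn, arm 1 vs arm 2 | D | Shift | Share of 2.1 |
|---|---|---|---|
| 7% vs 7% | any | 0 | 0% |
| 8% vs 6% | 7 | 0.02 × 7 = 0.14 | 7% |
| 9% vs 5% | 7 | 0.04 × 7 = 0.28 | 13% |
| 10% vs 4% | 14 | 0.06 × 14 = 0.84 | 40% |

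The shift favours the arm with more withdrawals. Each row supposes that every such student is withdrawn and all of their data are discarded, and that the excess lasts to the endpoint. A mixed model that keeps earlier scores would be affected less.

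**The case against.** A reader might infer that the protocol removes the worst outcomes and so favours the arm with more crises. The documents do not support that.

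- The 7.2 list is permissive. It does not require withdrawal on admission.
- The adverse-event item is not open to any event; it is tied to the participant's best interest.
- The one rule written specifically for psychiatric admission, in section 6.5, leads to premature termination with assessments continuing.
- Section 4.5 promises early terminators an end-of-study assessment, every randomised student stays in the intent-to-treat sample, earlier SSI scores stay in the mixed models, and section 8.3.2 records the admission as a serious adverse event.
- Hospitalisation is not itself the SSI outcome, so missing at random may fail but is not shown to fail. A directional bias needs unequal withdrawal or unequal severity between arms.
- The 7% comes from a different sample, and this trial excludes students judged at intake to be inappropriate for the centre because of imminent risk (section 5.2).

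These points stand, and they reduce the matter to a risk of unknown size. They do not remove it. Section 7.2 does not refer to section 4.5, and one closing assessment does not replace the remaining scheduled visits. A safety record supplies no later SSI or SITBI data.

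Assessments may themselves cause distress, as section 2.3.1 (Risk 3) acknowledges. An unconditional rule that they continue would therefore go too far.

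**Conclusion.** The point holds as an inconsistency in the current text with a plausible route to bias. Sections 7.2 (withdrawal list) and 2.3.3 conflict with sections 6.5 and 7.2 D, and with the commitments in sections 4.5, 6.1.3 and 9.3.1. Use of the withdrawal option can lose SSI and SITBI data for outcome-related reasons, and section 9 does not say how that would be handled, least of all for the primary Aim 1 comparison.

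The power cost is minor even if every such student were lost. The bias cannot be estimated from the documents. It is nil under equal withdrawal and severity; the figures of 0.28 and 0.84 points are illustrations for an analysis that drops these students, not forecasts. The case for acting rests on the contradiction and on how little it costs to remove. No view is taken on when study treatment should stop.

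**What to change.** Reconcile sections 2.3.3, 4.5, 6.5, 7.2 and 9.3.1 so that the end of study treatment and the end of assessments are two separate decisions, each recorded with its own date and reason. State in 7.2 that ending treatment for a listed event does not by itself end evaluator assessments. Scheduled assessments would still be sought through week 26 unless the student withdraws consent or dies, or the investigator documents that the assessments themselves are not in the student's best interest. Add investigator withdrawal to the attrition categories, and link it to the end-of-study assessment in 4.5. In section 9.3, state how outcomes missing after such an event are handled, for Aim 1 as well as for the mixed models.

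The cost is protocol wording and a small change to the disposition form. The visits are already scheduled (section 4.2), reimbursed (section 5.4) and possible remotely (section 8.2).
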